## RESEARCH PLAN

### A. BACKGROUND

Few medical injuries are more devastating to physical function and quality of life than the loss of a limb. Among Veterans, the loss of limbs (amputation) may occur from a diverse set of causes ranging from acute injuries suffered by soldiers in combat situations to increasingly common chronic diseases such as diabetes that disproportionately affect the Veteran population. Following amputations, the majority of patients report continuing sensations associated with the missing limb, referred to as phantom limb sensation. Phantom limb pain (PLP) is a specific phantom limb sensation that is experienced by up to 85% of patients with amputations. Amputees with PLP report poorer functioning, reduced quality of life, and greater psychological distress than amputees without PLP. Although there is some evidence that the severity of PLP decreases over time, the majority of patients continue to experience symptoms chronically. One study reported patients had experienced PLP for an average of 29 years. However, there is also evidence that frequency of episodes of PLP varies from over 20 days per month (34%) to 1 day per month (14%) and duration of episodes varies from seconds (38%) to continuous (12%). This indicates that PLP can vary on a day-to-day basis and may benefit from versatile approaches to assessment and treatment that can meet Veterans when and where PLP occurs.

Although traditional pain medication treatments are less effective for PLP, recent research offers promising possibilities for treating PLP. Ramachandran and Rogers-Ramachandran demonstrated that engaging in simple physical exercises while using a mirror to create the illusion of the missing limb altered participant's experience of their phantom sensations and in some cases even eliminated PLP. The authors argued that the mirror-fed visual input facilitates changes in neural activation that reduces the experience of PLP. Evidence from newer trials provides additional support and suggests that visual feedback from the mirror is a critical feature in pain symptom changes.

In order to provide validation for mirror therapy in a larger PLP trial, the current team of investigators obtained VA R&D support from 2008-2011 to carry out a clinical trial ([clinicaltrials.gov/show/NCT00731614](http://clinicaltrials.gov/show/NCT00731614)), comparing mirror therapy to a form of supportive psychotherapy designed to control for non-specific effects of treatment. Veterans receiving the mirror therapy treatment reported significant reduction in PLP, which was further maintained at 24 weeks post-treatment ( $F[10, 80]=2.26$ ,  $p=.024$  [unpublished data]). A limitation of the mirror therapy treatment was the reliance on self-reported changes in PLP sensations that required the participant's recall of symptoms from days or weeks prior. PLP differs from other forms of chronic pain in that it is usually intermittent in nature (In one study of amputees, 81% reported intermittent PLP in the prior month, and only 9% constant PLP in the prior month) rather than a constant sensation. In this study, we propose to extend our previously mirror therapy trial using immersive virtual reality (VR) technology that will allow Veterans to engage in the treatment in their natural living environment while simultaneously measuring the effectiveness of the treatment using real time assessment technology.

VR is a novel, technology-based treatment approach that preliminary research has shown to be effective for the management of acute and chronic pain. VR technology is usable by patients in non-clinical environments and includes assessment features that can allow for the real-time collection of data concerning device usage patterns and changes in PLP sensations during daily living circumstances. Several small studies have adapted visual feedback aspects of mirror therapy to VR treatments for PLP. Perry summarized four recent efforts in a 2014 review, with protocols using different motion sensor technology with the patient's intact limb to create an avatar in a simulated VR environment, where the patient engages in different exercises. Patients find these simulations engaging and often effective for PLP. Studies to date adapting visual feedback aspects of mirror therapy to VR, however, are small (5-14 patients), use mostly intermittent practice protocols, did not include Veterans, and employed only passive controls. In the current study, we propose to test a VR for PLP with 20 Veteran amputees using a daily practice protocol, real time assessments to monitor home-based PLP benefits, and will compare to an active control in the form of standard mirror therapy.

The proposed study will take place over a two year period comprised of a 1) a technical innovation and usability phase; and 2) a feasibility trial phase each lasting approximately twelve months.

Table 1. Overview of study proposal: methodology & outcomes.

Study phase	Sample size	Methodology	Primary outcomes
Technical innovation &	N=15	Iterative testing with participants using the VR equipment in order improve usability,	Satisfaction scores, usability ratings, problem reports, side

usability (year 1)		satisfaction, and effectiveness	effects, immersiveness
Feasibility trial (year 2)	N=20	Between groups design comparing VR treatment versus standard mirror therapy to estimate effects for larger scale trial	Adherence, satisfaction, changes in PLP, mood, function, quality of life

### SIGNIFICANCE

There is arguably no mission more central to the VA than improving the outcomes for combat-injured Veterans such as those with amputations. The VA system performs 10% of all amputations in the U.S., primarily in response to diabetes and vascular disease. Between 1989 and 1998, 60,324 Veterans had a lower limb amputation, with 62% being secondary to diabetes. Although amputation rates have decreased in the past decade, the total number of Veterans with amputations is likely to remain high with both the increased age of Veterans and the continuation of active military operations for the foreseeable future.

The proposed study will provide a novel, Veteran-tailored VR application towards PLP that we will evaluate in direct comparison to standard mirror therapy. The study represents a collaboration of senior VA pain researchers and VR development expertise. The design of the study will allow for rigorous testing among and feedback by Veterans with PLP in order to develop VR software promoting optimal patient accessibility as well as efficacy for pain symptom reduction and functional enhancement.

## B. RESEARCH DESIGN AND METHODS

### Overview

In the technical innovation and usability phase, we will develop VR software designed for the treatment of PLP and deploy this software with a pilot sample of Veterans with PLP for feedback concerning usability, side effects, and effectiveness. The research team includes the co-founder and chief technology officer ([name]) of Virtual Reality Medical Applications Inc., a San Diego-based company applying VR products to hospital settings. [name] prior experience with VR applications for healthcare settings will allow us to expand upon his existing VR applications and expedite the development of a VR treatment integrating mirror therapy components. This initial phase will include software development and interactive refinement of the VR software based upon feedback from a pilot sample of Veteran amputees with PLP. The feasibility trial phase will take place during year two of the proposal. In this phase, we will conduct a small scale two group clinical trial design with a pilot sample, evaluating the novel VR treatment relative to standard mirror therapy. Participants will receive either the VR or mirror therapy treatment for one month, with the treatments matched for in person visit frequency and homework frequency recommendations. The VR treatment will include real-time assessments of usage statistics and pain-related outcomes. The goal of the feasibility trial is to obtain preliminary efficacy data and obtain effect size and comparative effectiveness data for a larger trial application.

### Methods

**1. Participants and Enrollment.** In each year of the project, we will recruit samples of Veterans with PLP from primary care and amputee clinics. Co-investigator [name], NP, is the PACT (Primary Aligned Care Team) coordinator in the amputee clinic at the VA San Diego Healthcare System (VASDHS) and has specific recruitment experience with the PLP population from our previous R&D-supported clinical trial for PLP.

**2. Inclusion criteria.** 1) Ages 21-75 Veteran receiving care at VASDHS; 2) Upper or lower extremity amputation with reported PLP for at least six months; 3) PLP intensity  $\geq 4/10$ ; 4) English-speaking, literate, with stable residence; 6) Able to operate a VR headset as evidenced by direct observation. **3. Exclusion Criteria.** 1) Major medical illness that might confound effects of pain on function (e.g., advanced cardiac or pulmonary disease); 2) current active alcohol or substance use disorder as evidenced from medical record; 3) currently active suicidality, homicidality, or unstable psychiatric status in previous three months as measured by direct observation, patient self-report, or medical record; 4) moderate or severe cognitive impairment as demonstrated by medical diagnosis or clinical observation; 5) Prior mirror therapy experience.

### Patient Selection and Recruitment

Co-investigator [name], NP, is member of the VASDHS clinical staff and will meet with Veterans with amputations in the vascular, orthopedic, and amputee clinics as part of her clinical position and inform them about the study. [name] will attempt to contact every amputee receiving VASDHS services during the study period. If a patient expresses interest and agrees to be contacted, [name] will then provide the study coordinator with the patient's contact information. The coordinator will contact the patient, explain the study, obtain informed consent, and screen for PLP using the Trinity Amputation and Prosthetic Experience Scale.

### Women and Minorities

Approximately 37% percent of VA patients with amputations are minorities and we will attempt to sample minorities at or above this percentage in the pilot samples. Women may also be included. However,

because women comprise less than one percent of Veterans with amputations in the VA system^15 it is possible that no or few women will be eligible to participate in the study.

### **Recruitment Feasibility.**

The VA San Diego Healthcare System (VASDHS) currently provides care for over 450 Veterans with amputations, and up to 36 new Veterans a year undergo amputations in San Diego each year. Based upon our previous PLP trial, it is projected that dropout during will be ~ 10% and loss to follow-up will be modest (<10%). Allowing for 18 months for subject recruitment (see project timeline below). During the innovation and feasibility trial periods, we project that 4-5 subjects will be recruited per month. In our R&D PLP pilot study, 62.5% of amputees had PLP and 74% were willing to participate in the mirror therapy treatment. If we conservatively estimate that half of Veterans with PLP show frequency and severity of PLP symptoms sufficient to enroll, this project to approximately 150 amputees among the current population of 450 amputees enrolled at the VASDHS. Assuming we recruit just 20% of the eligible sample that will permit sufficient recruitment.

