### **Project Timeline**

Months 0-3: IRB approval; hiring of personnel; development of forms and database, recruitment

Months 3-12: VR software Development, Usability Testing (N=15), VR refinement

Months 13-24: Recruit and conduct feasibility trial (N=20); Months 21-24 will include data analyses, preparation of manuscripts and Merit Review applications for a larger VR treatment trial

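### On the current pool the plan describes, 20% uptake gives 28–30 Veterans against the 35 needed; counting new amputees makes it borderline at best

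*Combined protocol and SAP*

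**What the plan says.** All the recruitment inputs are in the Recruitment Feasibility section. The site "currently provides care for over 450 Veterans with amputations", and "up to 36 new Veterans a year undergo amputations in San Diego each year". From the earlier pilot, "62.5% of amputees had PLP and 74% were willing to participate in the mirror therapy treatment". The section then assumes that half of those with PLP are affected often and severely enough to enrol, and puts the eligible pool at "approximately 150 amputees among the current population of 450 amputees enrolled at the VASDHS". Its conclusion is: "Assuming we recruit just 20% of the eligible sample that will permit sufficient recruitment".

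On timing, the section begins "Allowing for 18 months for subject recruitment" and adds, for the innovation and feasibility trial periods together, that "we project that 4-5 subjects will be recruited per month".

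The sample sizes are elsewhere. The Project Timeline lists "Months 3-12: VR software Development, Usability Testing (N=15), VR refinement" and then a feasibility trial of N=20 in Months 13–24. The Year 1 procedures split the 15 into 10 alpha testers and 5 beta testers. The Year 2 procedures describe the 20 as a second sample, so the plan needs 35 different people.

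**The concern.** The sufficiency statement directly follows the pool estimate, so a reader will multiply the two. The product is below the total enrolment that the plan sets. A site that achieved exactly the stated uptake of the stated pool would finish the study short of its sample.

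The monthly projection raises a smaller question. Carried through the stated recruitment window, it gives a total far above both the 20% figure and the 35. The section does not say what the projection counts or how long it is meant to run.

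What is at stake is the planning justification. Recruitment rate is one of the feasibility items to be described under section C, Data Management and Statistical Analyses, so the planning figures that readers will have in mind should be right.

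**Working it through.** **Inputs.** From Recruitment Feasibility: 450 amputees in care; 62.5% with PLP; half of those sufficiently affected; uptake 20%; up to 36 new amputees a year; 18 months; 4–5 recruits per month; 74% willing. From Project Timeline and the Year 1 and Year 2 procedures: 15 + 20 = 35 separate participants. From Inclusion criteria: PLP for at least six months.

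**1. The plan's own pool.** 450 × 0.625 × 0.5 = 140.6, against a stated figure of about 150. Exactly 150 would need 150 / 0.3125 = 480 amputees. Adding one year of new cases gives 486 × 0.3125 = 151.9, which is close, but the text ties the 150 to the current 450. Both 140.6 and 150 are carried forward.

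**2. What 20% gives.**
- 0.20 × 140.6 = 28.1, which is 6.9 short of 35
- 0.20 × 150 = 30.0, which is 5 short of 35

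**3. Uptake needed for 35.**
- 35 / 140.6 = 24.9%
- 35 / 150 = 23.3%

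**4. Adding new amputees.** The low case uses the 0.3125 share and 18 months of accrual. The high case uses the one-third share implied by 150 of 450 and 24 months. The last two rows leave out the final six months of new cases, who could not yet have six months of PLP.

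| New cases counted | Pool | 20% of pool |
|---|---|---|
| Low, 18 months | 140.6 + 36 × 1.5 × 0.3125 = 157.5 | 31.5 |
| High, 24 months | 150 + 36 × 2 / 3 = 174 | 34.8 |
| Low, less six months | 140.6 + 36 × 1 × 0.3125 = 151.9 | 30.4 |
| High, less six months | 150 + 36 × 1.5 / 3 = 168 | 33.6 |

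The range is about 30–35. All four rows use 36 a year, which the plan gives as a maximum.

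**5. Size of the current population at which 20% would reach 35.**
- Without accrual: 35 / (0.20 × 0.3125) = 560, or 35 / (0.20 / 3) = 525.
- With accrual: from 525 − 72 = 453 (one-third share, 24 months) to 560 − 36 = 524 (0.3125 share, 12 months counted).

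**6. Attainability.** 0.74 × 140.6 = 104 and 0.74 × 150 = 111 willing Veterans; 35 is 34% or 32% of these.

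**7. The monthly projection.** 4 × 18 = 72 and 5 × 18 = 90. At that rate 35 is reached in 35 / 5 = 7 to 35 / 4 = 8.75 months. For Year 2 alone, 20 participants need 20 / 12 = 1.7 per month if enrolment uses all of Months 13–24. They need 20 / 8 = 2.5 if it closes by Month 20, and 20 / 7 = 2.9 if the four-week treatment must also finish by then. The documents do not fix the closing date.

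**The case against.** The strongest reply is that the pool is not a snapshot. The population is given as more than 450, new amputations are mentioned, and the Patient Selection and Recruitment section plans to approach every amputee served during the study period. On the most favourable accrual, 20% comes to 34.8, and about 453 current amputees would be enough. This stands as a limit on the concern: 20% is not shown to fail on every reading. It does not remove the concern, because the plan derives its pool from the current 450 and applies the 20% directly to it. With the six-month criterion the best case is 33.6.

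Two other rescues do not work. The 20% cannot be meant for Year 2 alone, since the section covers both the innovation and the feasibility periods. Nor can it be meant for all 281 Veterans with PLP (which would give 56), since the eligible sample has just been defined as about 150.

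Three stronger readings are tempting, and the documents support none of them:
- **That recruitment is infeasible.** An uptake of 23–25% is well below the 74% willingness cited.
- **That 4–5 per month contradicts N=35.** The plan never multiplies this rate by 18 months, and enrolment stops once the sample is reached. A projection above need is slack. What remains is that its meaning and duration are unclear.
- **That 35 / 18 = 1.9 per month is the benchmark for the feasibility report.** That figure pools both phases. Section C places recruitment rate under the Year 2 aims (N=20) and sets no target for it, and the Year 2 need is about 1.7–2.9 per month.

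**Conclusion.** The concern holds in a limited form. On the pool as stated, 20% uptake gives 28–30 Veterans, 5–7 short of 35; the uptake needed is 23–25%. With new amputees counted, 20% gives about 30–35, which is borderline at best. The monthly projection is a wording gap of secondary weight.

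The shortfall assumes that the current population is 450, though the plan gives this as a floor, and that 35 is the enrolment target. The range with accrual also assumes that new amputees qualify at the same rate as current ones. Nothing is added for the projected dropout of about 10%, because the plan does not say whether dropouts are replaced. Nothing is deducted for the other eligibility criteria, because the plan gives no figures for them. Reading the 74% as reassurance assumes that willingness in the earlier mirror therapy pilot carries over to this study.

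Severity is minor.

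**What to change.** Replace the sufficiency sentence in Recruitment Feasibility with something like: *About 140 Veterans are currently eligible (450 × 0.625 × 0.5); 35 participants across both phases require an uptake of about 25%.* If the pool is kept at 150, the figure is 23%. Alternatively, state that new amputees are counted, give the accrual period and how the six-month PLP criterion is applied, and report the resulting pool and uptake.

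For the monthly projection, say what the 4–5 counts (for example referred, screened or enrolled) and for how long it is expected to apply, or correct it. Do not add a pooled rate of 1.9 per month as a benchmark.

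The cost is one percentage and one or two sentences. Sample size, design, data collection and analysis are unchanged.

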### **Project Timeline**

Months 0-3: IRB approval; hiring of personnel; development of forms and database, recruitment

Months 3-12: VR software Development, Usability Testing (N=15), VR refinement

Months 13-24: Recruit and conduct feasibility trial (N=20); Months 21-24 will include data analyses, preparation of manuscripts and Merit Review applications for a larger VR treatment trial

### **Procedures**

#### **Year 1 Technical innovation and usability phase (Research Aim 1)**

The primary study goal in Year 1 is the development and refinement testing of a VR treatment for PLP. Our VR team experts [name] and [name], and a half-time VR technician will oversee the development of the VR-mirror therapy using state of the art Oculus VR headsets, specialized VR software available to [name] for treatment development purposes, and motion sensor equipment that will allow the VR staff to customize the VR exercises to the Veteran's missing limb. Among VR headset options, Oculus headsets represent a cost-effective option that incorporates the most recent VR technology advancements while maintaining costs at a level affordable by consumers (~\$500.00). We believe this choice is the best available for developing a VR treatment with practical applicability to a Veteran population. Following the initial software development (months 3-4; See Appendix 3 for illustrated description of VR development phases including images of currently developed VR environment), we will evaluate an alpha version of the VR protocol with 10 Veterans with PLP (months 5-10). Their participation will consist of laboratory visits to customize the software to their amputation location and train them with use of the VR headset over two weeks. We will collect feedback concerning patient satisfaction, effects on PLP, side effects, and immersiveness (Measures shown in Table 2) and open feedback that we will code qualitatively for analysis. The VR technician will contact them 2-3 times/week over their pilot test period. There is considerable usability data to date suggesting that VR technology is tolerated well by participants, including patients with chronic pain, for short term use. In the final two months of Year 1, we will test a beta version of the VR software with a second group of 5 Veterans with PLP. Their participation will be identical to the beta test group, with the goal of maximizing the immersiveness, usability, and benefits of the VR protocol as a Gold Master version for deployment in Year 2 of the study.

[figure not shown]
#### **Real-Time VR Embedded Pain Assessment.**

In addition to the development of the VR treatments, a second novel feature of the VR software is the incorporation of real-time PLP assessment and usability information at random intervals prior, during and after VR interaction. The VR assessments will not collect personal health information. Assessment data will be stored in the VR device during usage and connected by study identification number to the participant's database record for download during their in person visits. VR incorporates eye tracking technology that can allow a user to respond to questions about PLP, mood, immersiveness, or side effects using a visual analogue scale presented in the visual field, confirmed by participants' movements (e.g., a nod to confirm or head shake to disconfirm). Incorporation of a real-time pain assessment is merely an extension of the existing participant interaction system used to navigate VR menus, and so is straightforward to create. The ability to incorporate such ratings in the context of the VR protocol provides several compelling advantages over typical paper-and-pencil diary based methods for pain assessment, including 1) increasing validity by eliminating retrospective "backfilling", 2) assuring precise and time stamped collection of pre- and post-session pain intensity, and 3) provision of real-time feedback to participants, which may reinforce participation. Refining the real time assessment features will be part of the Year 1 goals. Dr.'s [name] and [name] each have substantial prior experience with the real-time assessment of psychosocial and behavioral factors.

